**Narrative Study Description**

*Randomization.* In this single-case randomization design, each participant will receive an equal number of sessions of visual-acoustic biofeedback and traditional treatment (n = 10 each), with randomized allocation of treatment types to individual sessions. Randomization will be blocked, with each week of treatment serving as a block; within each week/block, one session will be randomly assigned to feature visual-acoustic and one to feature traditional treatment.

*Intervention Delivery.* The text below describes elements of treatment that are shared across traditional and biofeedback conditions. All sessions will feature the same dosage of treatment and will follow the same structure. Treatment conditions will differ only in the nature of cues and feedback provided. Differences across treatment conditions are described below under **Interventions**. All treatment will be provided on an individual basis by a certified speech-language pathologist. Treatment will be delivered over Zoom videoconference calls using a unique password-protected room for each participant. The first 10 minutes of each session will consist of relatively unstructured, highly interactive pre-practice, designed to provide instruction on the phonetic requirements for /r/ and shaping strategies to transform the child's current productions into accurate /r/. The remainder of the session will elicit up to 150 syllables/words or 50 minutes of practice, whichever occurs first. (This level of intensity has been successfully achieved by members of our research team in previous and ongoing studies, including pilot studies of telepractice treatment.) Practice will occur in blocks of 10 consecutive trials on the same item (e.g., 10 /ra/), after which a new item will be addressed (e.g., 10 /re/). Within each block, the clinician will provide qualitative (knowledge of performance) feedback as prompted by our custom software.

In all conditions, stimulus presentation will be managed with our custom open-source software, Challenge Point Program (CPP). The CPP software prompts clinician actions such as delivery of knowledge of performance (KP) feedback, promoting increased fidelity in treatment implementation both within and across sites. It also enables systematic changes in practice difficulty based on participant performance. After the software presents a stimulus and the participant attempts to produce it, the clinician scores the response as 0 or 1 based on their clinical impression of an incorrect or correct production of /r/. Following each block of ten trials, the software automatically tallies the scores entered by the clinician and uses them to make adaptive changes in practice difficulty. When a participant demonstrates at least 80% cumulative accuracy at the session level, they will be advanced from syllable to word-level practice; if the cumulative session-level accuracy drops below 50%, they will be dropped back to the syllable level to decrease difficulty. In word-level practice, parameters are adjusted on a rotating basis so that as accuracy increases, either the frequency of feedback is reduced (80%-50%-20%-0%), clinician models are faded, or word shapes increase in complexity. Qualitative feedback (either biofeedback or verbal clinician feedback) will begin at 80% of trials and, contingent upon the participant's performance, will be systematically decreased to 0%.

**Primary Purpose:** Treatment

**Interventions**

*Intervention Type:* Behavioral

*Name:* Traditional articulation treatment

*Description:* Traditional articulation treatment involves providing auditory models and verbal descriptions of correct articulator placement, then cueing repetitive motor practice. Images and diagrams of the vocal tract will be used as visual aids; however, no real-time visual display of articulatory or acoustic information will be made available. Knowledge of performance feedback, when prompted by the CPP software, could describe either the desired articulator placement or the auditory quality of the target sound. Specific cues and strategies are publicly available as supplements to the published protocol of the parent study (McAllister, Preston, Hitchcock, Hill, 2020).

*Intervention Type:* Behavioral

*Name:* Biofeedback–visual-acoustic

*Description:* In visual-acoustic biofeedback treatment, the elements of traditional treatment (auditory models and verbal descriptions of articulator placement) are enhanced with a dynamic display of the speech signal in the form of the real-time LPC (Linear Predictive Coding) spectrum (Sona-Match module of KayPENTAX Sona-Speech software). Because correct vs incorrect productions of /r/ contrast acoustically in the frequency of the third formant (F3), participants will be cued to make their real-time LPC spectrum match a visual target characterized

by a low F3 frequency. They will be encouraged to attend to the visual display while adjusting the placement of their articulators and observing how those adjustments impact F3. Knowledge of performance feedback will typically involve reference to the location of the third peak on the visual display. Specific cues and strategies are publicly available as supplements to the published protocol of the parent study (McAllister et al., 2020).

**Study Phase:** Phase 1

**Intervention Model:** Other

**Masking:** Yes; Outcomes assessor

**Allocation:** Randomized

## Outcome Measures

**Name:** Acoustically measured accuracy of /r/ in syllables

**Type:** Primary

**Time Frame:** Before and after each session of treatment

**Brief Description:** Probes of words and syllables containing /r/ in various phonetic contexts will be elicited at the start and end of each treatment session. We will follow a semi-automated protocol developed in the parent project to demarcate intervals of interest in a Praat textgrid. Textgrids and recordings will be submitted to a forced aligner, followed by automated extraction of formant frequencies (F1, F2, F3) at the center of each /r/ interval identified. F3-F2 distance, which is smaller in correct /r/, will serve as the primary acoustic correlate of accuracy.

**Name:** Perceptually rated accuracy of /r/ production

**Type:** Secondary

**Time Frame:** Before Phase 0 and again after the end of all treatment (10 weeks later)

**Brief Description:** To assess generalization of treatment gains to untreated words, participants will read a 50-word probe and a 10-sentence probe list eliciting /r/ in various phonetic contexts. Stimuli in each probe will be presented individually in randomized order. No auditory models will be provided; for children with reading difficulty, semantic cues will be provided to elicit the intended word. Individual words will be isolated from the audio record of each word probe and presented in randomized order for binary rating (correct/incorrect) by 9 naive listeners who are blind to treatment condition and time point (but will see the written representation of each target word). Sentences will be rated in a similar fashion, but raters will hear the whole sentence and will be instructed to rate only a single word cued orthographically. We will use the proportion of “correct” ratings for each token (McAllister Byun, Harel, Halpin, & Szeredi, 2016) as our primary measure of perceptually rated accuracy.

## Subject Participation Duration

13 weeks (3 week baseline/maintenance, 10 weeks treatment)

## Will the study use an FDA-regulated intervention?

No

***Comparing Traditional and Biofeedback Telepractice Treatment for Residual Speech Errors
(C-RESULTS TPT)***

Protocol NCT04625062

Document generated July 1, 2020

Statistical Design and Power: C-RESULTS TPT

For inferential statistical analysis, a randomization test will be conducted for each participant. Randomization tests are computed within-subject, and we propose to replicate this comparison across 6 participants. Each randomization test will compare the two treatment types (traditional and visual-acoustic biofeedback) with respect to change in F3-F2 difference between pre-treatment and post-treatment probe in each session. In a previous randomization study comparing biofeedback and non-biofeedback treatment in 7 children with RSE (McAllister Byun, 2017), the median effect size of the difference between treatment conditions (d_2) was calculated to be 3.0. Calculations using GPower (Faul et al., 2007) indicate that our proposed within-participant comparison (10 observations in each condition) has 90% power to detect an effect of this magnitude. Relying on a precedent established in previous single-case studies of treatment efficacy (Maas & Farinella, 2012) and upheld throughout our own previous research (McAllister Byun & Hitchcock, 2012; McAllister Byun et al., 2014; Preston et al., 2014, McAllister Byun & Campbell, 2016; Preston et al., 2016; McAllister Byun, 2017), we will treat $d_2 = 1.0$ as the minimum difference between conditions that will be considered clinically significant. (That is, the difference between conditions must be at least as great as the pooled standard deviation). Our proposed within-participant comparison has power of .80 to detect this minimum effect size of interest. In addition, these power calculations ignore the fact that we will have multiple observations in each session; models that incorporate the nested structure of the data would presumably reflect higher power.

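### The power of .80 at d_2 = 1.0 does not follow from the SAP's pooled-SD definition of d_2, and it cannot come from the same calculation as the 90% at d_2 = 3.0

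*SAP*

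**What the plan says.** The SAP's only section, Statistical Design and Power, plans within-subject inference: "a randomization test will be conducted for each participant", replicated across 6 participants. The outcome compared is the pre-to-post change in F3-F2 difference in each session, with 10 sessions per treatment.

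Two power figures, attributed to GPower, are given for this within-participant comparison:

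- **At d_2 = 3.0.** From an earlier study in 7 children, "the median effect size of the difference between treatment conditions (d_2) was calculated to be 3.0". The design "has 90% power to detect an effect of this magnitude".
- **At d_2 = 1.0.** This value is taken "as the minimum difference between conditions that will be considered clinically significant", and it is explained in words: "the difference between conditions must be at least as great as the pooled standard deviation". For it the SAP says: "Our proposed within-participant comparison has power of .80 to detect this minimum effect size of interest".

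The Protocol (Narrative Study Description, Randomization) pairs the treatments by week: "within each week/block, one session will be randomly assigned to feature visual-acoustic and one to feature traditional treatment". Each participant therefore contributes 10 weekly pairs.

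Neither document states alpha, sidedness, the GPower test family, or a correlation between the two sessions of a week.

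**The concern.** Two things looked wrong.

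First, an effect of one pooled SD with 10 observations per condition does not normally give 80% power. A paired analysis can reach it, but then the effect has to be expressed in SDs of the within-week differences. Converting from the pooled SD to that scale requires the within-week correlation, which is not given.

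Second, the two figures do not fit together. Tripling the effect in the same test should carry power from .80 almost to 1, not to .90.

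The .80 is the only power figure at the SAP's own threshold of clinical significance, and the test is run separately in each child. It therefore governs how a non-significant result in one child is read. If the weekly sessions are uncorrelated, a child with a true d_2 of 1.0 has about an even chance of a non-significant two-sided test (1 − 0.514 = 0.486), not one in five.

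**Working it through.** **Inputs.** From the SAP: 10 observations per condition; d_2 on the pooled SD; stated powers of .80 at 1.0 and 90% at 3.0. From the Protocol: one session of each type per week, so n = 10 pairs. Assumed: alpha 0.05, with both sidedness cases shown; the SD is that of session-level values, since the SAP says its power figures ignore multiple observations within a session.

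**Formulas (noncentral t).**

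- Paired: df = 9, noncentrality = √10 × dz, where dz = d_2 / √(2(1 − ρ)) and ρ is the within-week correlation.
- Two-sample, ignoring the blocking: df = 18, noncentrality = d_2 × √(10/2).

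**Step 1: reproduce the .80.** Put dz = 1.0 in the paired test: noncentrality = √10 = 3.162 and two-sided power is 0.803. The SAP's figure is recovered, but the effect is now scaled by the SD of the differences. Setting dz = d_2 requires √(2(1 − ρ)) = 1, so ρ = 0.5. Solving for power of exactly .80:

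- two-sided: dz = 0.996, ρ = 1 − 1/(2 × 0.996²) = 0.496;
- one-sided: dz = 0.853, ρ = 0.313.

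**Step 2: power at d_2 = 1.0 on the SAP's definition.**

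| ρ | dz | Two-sided | One-sided |
|---|---|---|---|
| 0 | 0.707 | 0.514 | 0.662 |
| 0.25 | 0.816 | 0.634 | 0.769 |
| 0.5 | 1.000 | 0.803 | 0.898 |
| 0.6 | 1.118 | 0.881 | 0.946 |
| 0.7 | 1.291 | 0.951 | 0.982 |

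Ignoring the blocking, noncentrality = √5 = 2.236, with power 0.562 two-sided and 0.694 one-sided.

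**Step 3: d_2 detectable with 80% power.** Two-sided, d_2 = 0.996 × √(2(1 − ρ)): 1.41 at ρ = 0, 1.22 at 0.25, 1.00 at 0.5 and 0.89 at 0.6. One-sided at ρ = 0: 0.853 × √2 = 1.21.

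**Step 4: power at d_2 = 3.0.** Paired, ρ = 0: noncentrality = √10 × 3/√2 = 6.708, two-sided power 0.99996. Two-sample: noncentrality = 3√5 = 6.708, power 0.99999. A positive correlation raises the paired figure further. Neither is 90%.

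**Step 5: can one test give both figures?** In the paired test, 90% power needs dz = 1.155 two-sided (1.005 one-sided). If that corresponds to d_2 = 3.0, then d_2 = 1.0 is one third of it, dz = 0.385 (0.335), and power is 0.193 (0.253). The two-sample test gives 0.191 (0.252). Changing alpha does not help: in the two-sample test, a two-sided alpha of 0.0001 gives 0.918 at 3.0 but only 0.019 at 1.0.

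**Step 6: is the t approximation to blame?** The planned analysis is a randomization test. Simulating the exact within-week test over all 2^10 = 1,024 sign patterns (20,000 runs, normal data) gives 0.51, 0.63, 0.79, 0.88 and 0.95 two-sided for the five correlations in the table, and 0.67, 0.77, 0.90, 0.95 and 0.98 one-sided. At d_2 = 3.0 with ρ = 0 it exceeds 0.999. The approximation is sound.

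**The case against.** - **The .80 is a correct calculation.** It is, for a paired test with dz = 1.0, and at ρ = 0.5 the sentence is right as written. This stands, but the SAP defines d_2 on the pooled SD and gives no correlation, so the figure cannot be derived from what is stated.
- **Correlation is not the only unknown.** One-sided alpha 0.10 at ρ = 0 gives 0.802 paired and 0.817 unpaired. True, but nothing in the documents supports that alpha. The example shows again how much is left unstated.
- **90% may mean at least 90%.** On that reading it is not false. But the sentence reports the result of a calculation, and the reading leaves the .80 untouched. An understatement at 3.0 does no harm to the trial in itself.
- **The SAP expects more power from models of the nested data.** It offers that as a presumption without a figure, which cannot support .80. The SAP does not say over which observations the pooled SD is taken; session-level values are an assumption here.
- **The range stops at zero.** A negative within-week correlation is not excluded. At ρ = −0.25 two-sided power at d_2 = 1.0 is 0.43, so 0.51 is not a floor.
- **Only wording changes, and there are 6 participants.** Both are true. Replication tempers reliance on any one test, but the stated power is per participant and is how each child's result will be judged.

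**Conclusion.** The concern holds. Under alpha 0.05 and session-level values, a pooled-SD d_2 of 1.0 has power of .80 only at a within-week correlation of about 0.5 (two-sided) or 0.31 (one-sided). At correlation 0 it is 0.51 or 0.66; above 0.5, two-sided power is better than stated. This does not show that the study is underpowered: the SAP does not let a reader tell which case applies. The 90% at d_2 = 3.0 does not reproduce, and as a computed value it is incompatible with the .80. The practical problem is confined to the minimum effect, since the design is ample for the anticipated 3.0. Because both stated figures need restating, this should be corrected before the SAP is relied on.

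**What to change.** State the test, alpha, sidedness, the SD that scales d_2 and the assumed within-week correlation. If the test is two-sided at 0.05, replace the .80 sentence with:

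> With 10 weekly pairs and two-sided alpha 0.05, power for d_2 = 1.0 (pooled SD) is about 0.51 if the two sessions of a week are uncorrelated, 0.63 at a correlation of 0.25, 0.80 at 0.5 and 0.88 at 0.6; with uncorrelated sessions, 80% power is reached at d_2 of about 1.41. A non-significant result in one participant does not exclude d_2 = 1.0.

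Replace the 90% claim with:

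> more than 99.9% power at d_2 = 3.0 (two-sided alpha 0.05, within-week correlation of 0 or more)

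If the test is one-sided, say so and use 0.66, 0.77, 0.90 and 0.95 for the four correlations, with 80% power at d_2 of about 1.21 for uncorrelated sessions. If the team has a basis for one correlation, it should cite that basis and give the single matching figure.

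The cost is SAP wording only. The drawback is that the figure at d_2 = 1.0 becomes less favourable unless a correlation of about 0.5 or more (two-sided) can be supported.

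### Does the SAP's remark that nested models would have higher power leave the stated power of .80 resting on an unsupported margin?

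*SAP*

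**What the plan says.** The SAP specifies one inferential analysis: "For inferential statistical analysis, a randomization test will be conducted for each participant". The quantity compared is the "change in F3-F2 difference between pre-treatment and post-treatment probe in each session". Power is given for "our proposed within-participant comparison (10 observations in each condition"), and is stated as .80 at d_2 = 1.0, the smallest difference treated as clinically significant. The SAP explains that threshold by saying that "the difference between conditions must be at least as great as the pooled standard deviation", without saying whether the SD is that of session values or of single tokens.

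The Protocol (Narrative Study Description, Randomization) sets 10 sessions of each type per participant, and "within each week/block, one session will be randomly assigned to feature visual-acoustic and one to feature traditional treatment". Under Outcome Measures, the primary outcome comes from many tokens: "Probes of words and syllables containing /r/ in various phonetic contexts will be elicited at the start and end of each treatment session".

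The SAP then closes with the remark at issue, that "models that incorporate the nested structure of the data would presumably reflect higher power". It gives no tokens per probe, ICC, variance components or model specification.

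**The concern.** The remark presents .80 as a conservative figure. The unit of randomisation is the session, and the 10 observations per condition match the 10 sessions per condition exactly. If d_2 is scaled by the SD of session change scores, that SD already contains the token noise after averaging over the probe. Counting the tokens again in a nested model adds no new sessions, so the promised margin may not exist.

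The remark also speaks of models, while the specified analysis is a randomization test. If a reader relied on the margin, the design could look safer than it is. A careless reading could also invite a token-level analysis that ignores sessions.

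**Working it through.** **Inputs.** From the documents: 10 sessions per condition, 10 weekly pairs, d_2 = 1.0, stated power .80. Not in the documents and therefore assumed: two-sided alpha 0.05, m tokens per session, and ICC (the share of token-level variance that lies between sessions).

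**1. The plan's own figure.** For a two-sided paired t-test on 10 pairs, with a standardised mean difference of 1.0, the noncentrality is 1.0 × √10 = 3.162 on 9 df, with critical value 2.262. Power is 0.803, which reproduces .80. An unpaired 10 v 10 t-test has noncentrality 1.0 × √(10/2) = 2.236 on 18 df and power 0.562. The unpaired figure serves below only as a baseline for measuring gains. Which scaling suits d_2 is a separate matter.

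**2. Session-level d_2, balanced tokens.** With token variance set to 1, the variance of a session mean is ICC + (1 − ICC)/m. With equal m, the nested estimate of the treatment difference is the difference of session means. The nested F is the mean square for condition over that for condition-by-week, on 1 and 9 df, and it equals the square of the paired t on session means.
- In simulated data the two p-values differ by less than 1e-15.
- The week-blocked randomization test over all 2^10 = 1024 assignments gives identical p-values from tokens and from session means.
- A REML random-intercept model with 20 tokens per session has power 0.567, 0.567 and 0.558 at ICC 0.05, 0.2 and 0.5. The session-mean test has 0.568, 0.567 and 0.558.

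The gain is zero.

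**3. Session-level d_2, unequal tokens.** The most a nested model can gain, with variances known, is the ratio of the unweighted to the optimally weighted variance. The effective d is the square root of that ratio.

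| Tokens per session | ICC | Variance ratio | Unpaired power (from 0.562) | Paired power (from 0.803) |
|---|---|---|---|---|
| 15–25 | 0.05 | 1.006 | 0.564 | 0.805 |
| 5–35 | 0.2 | 1.014 | 0.568 | 0.808 |
| 5–35 | 0.05 | 1.089 | 0.598 | 0.835 |
| 5–35 | 0 | 1.298 | 0.674 | 0.892 |

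**4. Session-level d_2, items that vary between probes.** Suppose half the within-session variance is due to items and the model removes it fully.
- m = 10, ICC 0.1: variance falls from 0.1 + 0.9/10 = 0.190 to 0.1 + 0.45/10 = 0.145. The ratio is 1.310, d is 1.145, and unpaired power goes from 0.562 to 0.678.
- m = 25, ICC 0.3: variance falls from 0.328 to 0.314. The ratio is 1.045, d is 1.022, and power is 0.580.
- If every probe uses the same items, this gain vanishes.

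**5. Token-level d_2.** The session-level effect is then 1/√(ICC + (1 − ICC)/m). With m = 20 it is 2.04 at ICC 0.2, 1.38 at ICC 0.5 and 1.00 at ICC 1. Unpaired power is 0.991, 0.831 and 0.562. The remark is correct for any ICC below 1.

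**The case for a change.** The strongest case for acting is that the sentence cannot be checked from what the SAP gives, and that on the most natural reading with balanced probes it is wrong. It closes the power section, so a reader may take .80 as a floor. The SAP also never says how the tokens of a probe become one value per session, so the unit of analysis has to be inferred. Deleting the sentence would cost nothing.

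The algebra stands, and so does the point that the remark is unquantified. Three things weaken the rest. First, the SAP names no level for the pooled SD, so the remark is not demonstrated rather than shown to be false. Second, even with a session-level d_2, steps 3 and 4 show conditions in which a nested model does gain. Third, the unit of analysis is not seriously in doubt: change per session, 10 observations per condition and session-level randomisation all lead an analyst to one post-minus-pre value per session, 20 per child. The SAP proposes no token-level test that ignores sessions, so a rule about such a test would govern an analysis that is not planned.

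**Conclusion.** The remark is unquantified and should not be read as a safety margin. With a session-level d_2, equal token counts and the same items in each probe, nesting adds nothing. With strongly unequal counts or varying items, the assumed cases above add from under 1 to about 12 percentage points (0.562 to at most 0.678, unpaired). With a token-level d_2 the gain can be larger. These sizes rest on assumed alpha, token counts and ICCs.

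No change to the plan follows. The sentence is explicitly hedged, and the stated .80 is computed without it. The number of sessions, the 6 participants, the randomization test and the d_2 = 1.0 threshold would all be the same if it were struck out. Averaging each probe's tokens into one session value is a detail that analysts will fill sensibly. Whether .80 is itself the right figure for a d_2 scaled by the pooled SD is a different question and is not settled here.
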